6.9 Subgroup Analyses

Primary efficacy will be summarized for the following subgroups: HCA (Y/N), IV contrast within 48hrs prior to surgery (Y/N), biological sex (M/F), age (Age<65, Age \geq 65), baseline diabetes mellitus (Y/N), baseline heart failure (Y/N), and baseline hypertension (Y/N).

The outcome of interest will be AKI severity of 0 versus AKI severity of 1/2/3 at 48 hours. Logistic regression will be used to determine the odds ratio for SoC+ CytoSorb versus SoC within each subgroup. The odds ratio and associated 95% confidence intervals for each subgroup will be presented in a forest plot. The analysis will be repeated but with the outcome being AKI severity of 0 or 1 versus AKI severity of 2 or 3.

Analyses will be performed in the ITT population (excluding Roll-ins). These analyses are intended to demonstrate consistency of results across subgroups.

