Study Population	
 
The population evaluated for effectiveness in the treatment group will consist of a primary sub-population and a secondary sub-population.
 
The primary sub-population includes all subjects enrolled and randomized to the treatment group who are undergoing valve replacement with another procedure (e.g., CABG and valve replacement) without Hypothermic Circulatory Arrest (HCA)
 
The secondary sub-population consists of all surgical subjects undergoing aortic reconstructions with or without other procedures (e.g., CABG, valve replacement) with HCA
 

Sample Size	40 investigational sites in the United States. A roll-in cohort of up to 80 additional subjects may be enrolled in the study and assigned to treatment with CytoSorb device.
Duration of participation for each patient	Primary, secondary, and exploratory endpoints will be evaluated on the day of cardiac surgery up to Day Seven (7) post-cardiac surgery or through hospital discharge, whichever occurs first. Subjects will be followed through 30-day follow-up visit to fully evaluate safety (AEs will be followed through study exit and device-related SAEs will be followed until a return to a stable state as determined by the investigator).
Patient treatment	Two devices, configured into a parallel circuit are placed between the oxygenator and the venous reservoir and run as a bypass shunt to the main blood flow in a standard heart-lung machine. The first device will be introduced at t=0 (start of CPB). The second device will be introduced at t=90 minutes after the start of CPB.
Study Objectives:	To evaluate the safety and performance of the CytoSorb ® device to decrease the incidence or severity of AKI in the first 48 hours after surgery when used intraoperatively with cardiopulmonary bypass (CPB) in subjects undergoing cardiac surgery. The study hypothesis is that, for patients at increased risk for AKI based upon use of the Cleveland Clinic Score for stratification of the risk of cardiac surgery associated AKI (CSA-AKI), the intra-operative usage of the CytoSorb ® device in addition to the standard of care in a bypass circuit during cardiopulmonary bypass will decrease the incidence or severity of AKI per the Kidney Disease Improving Global Outcomes (KDIGO) clinical practice guideline definition of acute kidney injury.

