### 11.1.2 Effectiveness evaluations:

The primary endpoint will be assessed in each modified intent-to-treat (mITT) population in step-wise fashion beginning with the primary sub-population. If a significant beneficial effect is met for CytoSorb over control at a one-sided overall 0.025 level of significance, then the study will be considered to be a primary endpoint statistical success on this subpopulation and testing will proceed to the secondary sub-population. Otherwise the study will be considered to have statistically failed the primary endpoint.

We have selected to use a modified intent-to-treat population (mITT) population to avoid the consequence of including patients that were excluded from the study after randomization due to administrative reasons.

Use of the mITT population as defined is not anticipated to result in bias or informative censoring of the data.

The primary endpoint (rank order presence and severity of AKI) will be compared between treatments with Wilcoxon Rank Sum test. Continuous endpoints will be assessed via ANCOVA with baseline value as covariate. Binary endpoints will be assessed via unconditional exact binomial test. The primary endpoint will be summarized by subgroup factors, e.g., those who receive IV contrast within 48 hours prior to surgery versus those who do not. Additionally, subgroup-by-treatment interaction may be tested via generalized ordered categorical model and/or for binary combinations of outcomes (e.g., presence / absence of any AKI, and/or severe AKI) by logistic regression. Details will be in the SAP.

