4.1 Study Design Changes

The study was stopped early at the discretion of the sponsor, prior to any interim analyses being performed. Total enrollment, including roll-ins reached 151 subjects of the planned 420. Analyses described within this SAP reflect those that will be performed for the final report that includes results

| Statistical Analysis Plan | | Ра | ge 9 of 19 |
|---------------------------|---|----|------------|
| Sponsor | Study | | Version |
| CytoSorbents | ts CytoSorb [®] REduction of FREe Hemoglobin/Acute Kidney Injury (AKI) during Cardiac Surgery | | 1.0 |

from the 151 patients and may not reflect those originally planned for the total study population as stated in the CIP.

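### SAP 6.9 aims to show that the effect is consistent across subgroups, but plans no estimate of the between-subgroup difference and no method for sparse Stage 2-3 cells

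*SAP*

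**What the plan says.** SAP 6.9 lists seven two-level factors: HCA, IV contrast within 48 hours before surgery, sex, age, diabetes, heart failure and hypertension. The outcome of interest is any AKI against none at 48 hours. On method: "Logistic regression will be used to determine the odds ratio for SoC+ CytoSorb versus SoC within each subgroup". The odds ratios and their 95% CIs go into a forest plot. Then: "The analysis will be repeated but with the outcome being AKI severity of 0 or 1 versus AKI severity of 2 or 3". That makes 7 × 2 × 2 = 28 odds ratios. The stated purpose is: "These analyses are intended to demonstrate consistency of results across subgroups".

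Section 6.9 gives no treatment-by-subgroup estimate, no minimum cell count and no rule for empty cells. Protocol 11.1.2 had said that "subgroup-by-treatment interaction may be tested via generalized ordered categorical model", or by logistic regression for binary outcomes, and left the details to the SAP.

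On size, SAP 4.1 reports: "Total enrollment, including roll-ins reached 151 subjects of the planned 420". SAP 6.9 excludes roll-ins from the subgroup analysis.

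**The concern.** Consistency is a statement about how far the treatment effect differs between levels of a factor. A column of separate odds ratios does not measure that. With a few dozen patients per arm, the estimates will scatter even when the true effect is identical everywhere. Equally, intervals this wide overlap whatever the truth is. The display can therefore be read as consistency or as heterogeneity, and the plan gives the reader nothing to judge it by.

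HCA matters most. It is a stratification factor (protocol 8.5.1, SAP 4.2) and it separates the protocol's primary and secondary efficacy sub-populations (protocol 11.1). SAP 6.2 keeps only the ITT and Safety populations, so 6.9 is the one place where efficacy is planned by HCA.

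A second problem concerns Stage 2-3. Ordinary logistic regression has no finite odds ratio when an arm has no events or only events, and the SAP does not say what happens then.

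**Working it through.** **Inputs.**
- AKI rates, protocol Table 5. Control: any AKI 76%, Stage 2-3 29%. CytoSorb Example 1: 64% and 11%. CytoSorb Example 2: 56% and 16%.
- Randomised N: not stated. The 151 enrolled include roll-ins, and the protocol synopsis says: "A roll-in cohort of up to 80 additional subjects may be enrolled in the study and assigned to treatment with CytoSorb device". I assume 151 − 80 = 71 to 151 − 2 = 149, the upper value being one site's two roll-ins. Enrolment is defined by consent, so even 71 is not a strict floor.
- Prevalences: protocol 11.2 implies at most about one third with HCA. The others are not given and are assumed.

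**1. Check that the Table 5 rates are usable.** Two-proportion power, pooled variance under the null, one-sided 0.025, 133.5 per arm. For Example 1, any AKI: SE0 = √(2 × 0.70 × 0.30 / 133.5) = 0.0561; SE1 = √((0.76 × 0.24 + 0.64 × 0.36) / 133.5) = 0.0556; power = Φ((0.12 − 1.96 × 0.0561) / 0.0556) = 0.572. Table 5 states 0.57. The other three give 0.961, 0.936 and 0.723, against 0.96, 0.94 and 0.72. All reproduce.

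**2. Precision within a level.** With n per arm, SE(log OR) = √(1/[n·pC(1 − pC)] + 1/[n·pT(1 − pT)]). The Example 1 any-AKI odds ratio is (0.64/0.36)/(0.76/0.24) = 0.56.
- N=149, level of one half, n=37.25: SE 0.514, 95% CI about 0.21 to 1.54, upper/lower ratio 7.5.
- N=71, level of one third, n=11.8: SE 0.911, 95% CI about 0.09 to 3.35, ratio 35.6.
- Stage 2-3 over the same range: ratio 12 to 83.

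**3. Wrong-way estimates under a uniform effect.** For a half-sample level, P(OR > 1) = Φ(ln 0.56 / SE). This is Φ(−0.577/0.514) = 13% at N=149 and Φ(−0.577/0.744) = 22% at N=71. Simulating seven independent factors, with the smaller level assumed to hold 25-40% of patients, at least one of 14 levels points the wrong way for any AKI in roughly 60-75% of trials under Example 1 and about 33-55% under Example 2.

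**4. Inestimable odds ratios.** Per level, P(an empty cell) = 1 − [1 − pT^n − (1 − pT)^n] × [1 − pC^n − (1 − pC)^n]. At n=12 under Example 1:
- any AKI: 1 − (1 − 0.64^12)(1 − 0.76^12) = 1 − 0.9953 × 0.9629 = 4% (the remaining terms are negligible);
- Stage 2-3: 1 − (1 − 0.89^12)(1 − 0.71^12) = 1 − 0.753 × 0.984 = 26%.

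Averaged over random subgroup sizes, N 71-149, both examples:

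| Level holds | Any AKI | Stage 2-3 |
|---|---|---|
| 1/2 | 0-1% | 0.2-14% |
| 1/3 | 0.2-6.5% | 2-29% |
| 20% | 3-25% | 10-53% |
| 10% | 21-65% | 39-82% |

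In the simulation, at least one of the 14 Stage 2-3 odds ratios is inestimable in about 12-35% of trials at N=149 and 67-83% at N=71.

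**5. What an interaction estimate could show.** SE of the log ratio of odds ratios = √(SE1² + SE2²), where SE1 and SE2 belong to the two levels. At N=149, split in half, any AKI: √(0.514² + 0.514²) = 0.726. Two-sided 0.05 power for a two-fold ratio is Φ(0.693/0.726 − 1.96) = 16%. Across N 71-149, splits of 1/3:2/3 or 1/2:1/2 and both outcomes, power is about 7-16% for a two-fold ratio and 12-33% for a three-fold ratio.

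**The case against.** The case for leaving the section alone has weight.

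- The protocol's interaction test was optional, and the SAP says openly that its analyses may differ from the protocol because the trial stopped early. A reader might infer that a promised test was withdrawn. The documents do not support that: an option was not exercised.
- A reader might infer that undefined estimates will be common throughout. They will not. For any AKI, the SAP's outcome of interest, they are uncommon unless a level is small. The problem lies mainly with Stage 2-3.
- The text does not say that separate models are fitted. A model with treatment, subgroup and their interaction, and no other covariates, returns the same within-level odds ratios. The HCA-specific estimates are imprecise, not invalid, and match the protocol's stepwise structure.
- Section 6.9 plans no p-values or significance rule, so nobody is told to contrast significant with non-significant levels.
- Interaction power is so low that a non-significant p-value is likely either way, and could itself be misread as consistency.
- SAP section 7 allows justified changes for data characteristics, which could cover sparse cells.

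All of this limits the point, but it does not supply the missing estimate. The stated aim still exceeds what the planned display can show, and section 7 permits a sparse-cell method without specifying one.

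**Conclusion.** The point holds in a limited form. Section 6.9 cannot meet its stated aim: it never estimates the between-level difference, and its within-level estimates are too imprecise to show consistency. Under a uniform effect on any AKI, at least one wrong-way level is expected in roughly 60-75% of trials (Example 1) or 33-55% (Example 2). For Stage 2-3, at least one inestimable odds ratio is a real possibility at N=149 and likely at N=71.

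These figures rest on Table 5 rates, an assumed 71-149 randomised, independent factors and assumed prevalences. The actual frequencies cannot be fixed from the documents. Treating 151 as the analysed number would be wrong, because that total includes roll-ins. These are secondary displays, and no primary conclusion depends on them.

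**What to change.** Amend SAP 6.9 before the analysis, as section 7 provides:

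1. For each factor, HCA first, fit one model with treatment, subgroup and their interaction. Report the ratio of odds ratios with its 95% CI beside the within-level odds ratios. Give the interaction p-value as secondary.
2. Use Firth-penalised or exact logistic regression for the Stage 2-3 outcome.
3. Reword the aim as descriptive and exploratory, and state that a non-significant interaction is not evidence of consistency.

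The cost is a few sentences and a few lines of code. The downside is an imprecise estimate: even in the best case of step 5, the CI for the ratio of odds ratios spans exp(3.92 × 0.726), about a 17-fold range. The SAP should state this and the low interaction power.

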6.10 Protocol Deviations

A protocol deviation is a failure to comply with the requirements specified within the clinical study protocol.

The protocol deviations for this study consist of, but not limited to the following:

- Failure to obtain subject's informed consent prior to any study-related activities
- Failure to conduct protocol required clinical follow-ups
- Failure to conduct protocol required clinical follow-ups within time windows
- Failure to report serious adverse events according to protocol requirements.

Protocol deviations will be classified as either minor or major. A major protocol deviation is any deviation that could impact subject safety or the integrity of the trial.

The sponsor, or designee, will be responsible for producing the final protocol deviation file (formatted as a Microsoft Excel file) with major/minor classification, which will be finalized prior to database lock. This file will include site, subject ID, deviation date, deviation category, deviation type (major/minor), and a description of the protocol deviation.

| Statistical Analysis Plan Pa | | ge 18 of 19 | |
|------------------------------|---|-------------|---------|
| Sponsor | Study | | Version |
| CytoSorbents | CYTOSORB [®] REDUCTION OF FREE HEMOGLOBIN/ACU INJURY (AKI) DURING CARDIAC SURGERY | te Kidney | 1.0 |

The number and percentage of treated subjects with major protocol deviations will be summarized by deviation category, treatment group and overall. Deviation types will be presented in alphabetical order.

7 Changes from Planned Analyses

Any changes to planned statistical analyses determined necessary prior to performing the analyses will be documented in an amended Statistical Analysis Plan and approved prior to the analysis when possible. Any other deviations or changes from the planned analyses deemed necessary due to violation of critical underlying statistical assumptions, data characteristics, or missing data will be clearly described in the clinical study report with justification and rationale.

| Statistical Analysis Plan Pa | | ge 19 of 19 | |
|------------------------------|---|-------------|---------|
| Sponsor | Study | | Version |
| CytoSorbents | CYTOSORB [®] REDUCTION OF FREE HEMOGLOBIN/ACU INJURY (AKI) DURING CARDIAC SURGERY | te Kidney | 1.0 |

8 References

